**Table 7-3 Anticipated Recruitment Timetable and Sample Sizea,b**

Year 1	Year 2	Year 3	Year 4	Year 5	Year 6	Year 7
Enroll	Enroll	Enroll	Enroll	Enroll	Enroll	Enroll
34 Exposed	36 Exposed	36 Exposed	36 Exposed	36 Exposed	36 Exposed	36 Exposed
34 DMC	36 DMC	36 DMC	36 DMC	36 DMC	36 DMC	36 DMC
34 HC	34 HC	34 HC	36 HC	36 HC	36 HC	36 HC

aDisease-matched comparison (DMC)

bHealthy comparison (HC)

### 7.5.1 Determination of sample size

The sample size for this study is not only based on the statistical considerations to address the question of interest but also takes into account the feasibility aspects, prior experience and available literature ([Krueger et al 2017](#)) on conduct of pregnancy registries in the MS disease area.

In the three cohorts, approximately 867 pregnant women will be enrolled in US and Canada with a ratio of 1:1:1.

Based on previous experience with MotherToBaby/OTIS Pregnancy Studies, it is estimated that subjects will be an average of 7-10 weeks post-LMP at the time of enrollment. Given this mean gestational timing at enrollment, the anticipated spontaneous abortion/stillbirth rate is 10%, the estimated elective abortion rate is 5%, and the estimated lost to follow-up rate is 5% ([Chambers et al, 2016](#)). This will result in known outcomes for approximately 273 pregnancies in each cohort, including 231 pregnancies with at least one live born infant in each cohort at the end of recruitment.

Baseline rates of major structural birth defects, specific patterns of three or more minor structural defects, premature delivery, and small for gestational age are based on previous MotherToBaby/ OTIS studies and on general population data. Rates of spontaneous abortion in the general population are 15-20% ([Avalos AL, et al 2012](#), and [Magnus et al 2019](#)). However, since women do not typically enroll in pregnancy registries until after 7-8 weeks' gestation when the highest risk of spontaneous abortion has passed, the baseline estimate is drawn from previous OTIS studies. [Table 7-4](#) gives the minimum detectable effect sizes with 80% power (two-sided significance level 0.05, except as noted below for pattern of minor structural defects), for the comparisons described above. If the disease-matched comparison and the healthy comparison groups are comparable, then consideration will be given to pooling data in the two comparisons cohorts for analysis, as shown in [Table 7-5](#). The current sample size provides 80% power to detect a risk ratio of approximately 4.4 or greater in major structural defects compared to the baseline prevalence of 3% in the comparison groups. This is consistent with the population prevalence of major structural defects of 2.8% in the Atlanta metropolitan area ([CDC 2017](#)).

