## Study size

The prospective cohort study target sample size is 289 pregnant women who have been exposed to siponimod in pregnancy (i.e. on or any time after the 4th day post first day of the LMP prior to conception), for MS, 289 pregnant women diagnosed with MS not exposed to siponimod during pregnancy (primary comparison group/comparison group 1), and 289 healthy women i.e. women who are not diagnosed with MS, or any other autoimmune disease, and without exposure to siponimod, or any known human teratogen during pregnancy (secondary comparison group/comparison group 2).

The current sample size provides 80% power to detect a risk ratio of approximately 3.0 or greater in major structural defects with reference to the baseline prevalence of 2.8% in the Atlanta metropolitan area ([CDC 2017](#)).

Up to an additional 50 women will be enrolled in an exposure series group. This is a group of women with exposure to siponimod during pregnancy, but who do not meet eligibility criteria for the siponimod-exposed cohort group (e.g. retrospective cases would be in this group).

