**Table 7-4 Sample Size and Detectable Effect Size with 80% Power for Comparison of Exposed Cohort 1 to Unexposed Cohort 2**

Endpoint	N per group	Rate in comparison group	Relative risk	Power
Major structural defects b	231	3%	3.0	80%
Specific pattern of 3 or more minor structural defects	231	1%	4.6	80% c
Spontaneous abortion/still birth	259	10%	1.9	80%

Endpoint	N per group	Rate in comparison group	Relative risk	Power
Preterm delivery	231	10%	1.9	80%
Small for gestational age	231	10%	1.9	80%

aAll tests are two-sided with alpha = 0.05, based on Fisher's exact test, unless specified otherwise. Calculations conducted using R.

bPrimary endpoint; among livebirths.

cOne-sided

**Table 7-5 Sample Size and Detectable Effect Size with 80% Power for Comparison of Exposed Cohort 1 to Unexposed Cohorts 2 and 3 Combined**

Endpoint	N in exposed group	N in comparison group	Rate in comparison group	Relative risk	Power
Major structural defects b	231	462	3%	2.7	80%
Specific pattern of 3 or more minor structural defects	231	462	1%	4.0	80% c
Spontaneous abortion/still birth	259	518	10%	1.7	80%
Preterm delivery	231	462	10%	1.8	80%
Small for gestational age	231	462	10%	1.8	80%

aAll tests are two-sided with alpha = 0.05, based on Fisher's exact test, unless specified otherwise. Calculations conducted using R.

bPrimary endpoint; among livebirths.

cOne-sided

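### Section 7.5.1 gives a detectable risk ratio of 4.4 for the primary outcome; Table 7-4 and the Abstract give 3.0 for the same design

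*Protocol*

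**What the plan says.** Three places in the protocol state the detectable risk ratio (RR) for the primary outcome.

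- **Section 7.5.1, text:** "The current sample size provides 80% power to detect a risk ratio of approximately 4.4 or greater in major structural defects". The rate assumed for unexposed pregnancies is 3%.
- **Section 2 (Abstract), Study size:** "The current sample size provides 80% power to detect a risk ratio of approximately 3.0 or greater in major structural defects". Here the assumed rate is 2.8%, taken from the Atlanta surveillance programme.
- **Table 7-4 (in Section 7.5.1), titled** "Sample Size and Detectable Effect Size with 80% Power for Comparison of Exposed Cohort 1 to Unexposed Cohort 2": the row for major structural defects lists 231 per group, a 3% comparison rate, a relative risk of 3.0 and 80% power. The footnote says the tests are two-sided at 0.05 and based on Fisher's exact test.

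The design behind these figures is stated once. Section 7.5.1 says that "approximately 867 pregnant women will be enrolled in US and Canada with a ratio of 1:1:1", which is 289 per cohort, "including 231 pregnancies with at least one live born infant in each cohort at the end of recruitment". Table 7-5, which pools the two comparison cohorts (231 against 462), gives 2.7.

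**The concern.** The text of Section 7.5.1 and the table it introduces disagree on the same quantity for the same design. At a 3% baseline, an RR of 3.0 means a defect rate of 9% in exposed pregnancies, and an RR of 4.4 means 13.2%. A reader of the text would conclude that the registry has 80% power only from a rate of 13.2%. A reader of the table would conclude 9%, and a reader of the Abstract 8.4% (3.0 × 2.8%).

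The registry is run to fulfil a post-marketing requirement, and the detectable RR is its planned sensitivity on the primary outcome. The year-three feasibility assessment in Section 7.5.2 also asks whether the question can be answered with the target sample size. That judgement needs a single stated sensitivity.

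**Working it through.** **Inputs** (Section 7.5.1 and the Table 7-4 footnote): 231 live-birth pregnancies per group, comparison rate p0 = 3%, two-sided alpha 0.05, power 80%, Fisher's exact test. Losses are 10% + 5% + 5%, and 289 × 0.80 = 231.2, so 231 does follow from 289 enrolled.

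**Step 1. Reproduce the 3.0 of Table 7-4.** The arcsine approximation is n = 2(1.960 + 0.842)² / h², with h = 2·asin√p1 − 2·asin√p0. For p1 = 9% and p0 = 3%:

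- h = 0.6094 − 0.3482 = 0.2612
- n = 15.70 / 0.0682 = 230.05, rounded up to 231
- 231 / 0.80 = 288.75, rounded up to 289

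At 231 per group the arcsine power for RR 3.0 is 80.2% and the detectable RR is 2.99. The 3.0 and the enrolment of 289 therefore belong together.

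**Step 2. Test 4.4 at 231 per group.** Here p1 = 4.4 × 3% = 13.2%. Exact Fisher power is the sum of Bin(x; 231, p1) × Bin(y; 231, p0) over all tables whose two-sided Fisher p-value is at most 0.05.

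| Method | Power at RR 4.4 | Power at RR 3.0 | RR with 80% power |
|---|---|---|---|
| Fisher exact | 98.3% | 74.0% | 3.18 |
| Pooled normal | 98.2% | 77.7% | 3.08 |
| Arcsine | 98.9% | 80.2% | 2.99 |

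No method makes 4.4 an 80%-power figure.

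**Step 3. Look for a reading that gives 4.4.**

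- 2.8% baseline, 231 per group: RR 3.09 (arcsine), about 3.3 (Fisher).
- Pooled comparators, 231 against 462: RR 2.67 (arcsine), 2.71 (Fisher).
- One-sided Fisher, 231 per group: RR 2.89.
- Other denominators, two-sided Fisher at 3%: RR 3.01 at 259 per group, 2.94 at 273, 2.89 at 289.

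None comes near 4.4.

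**Step 4. Find the group size that 4.4 fits.** For 13.2% against 3%, h = 0.7437 − 0.3482 = 0.3955, so n = 15.70 / 0.1564 = 100.4 per group by arcsine. At exactly 100 per group, arcsine power is 79.9% and the detectable RR is 4.41. At the planned 20% loss, 100 live births correspond to 100 / 0.80 = 125 enrolled per cohort. The pooled normal formula needs 112 per group and Fisher's test about 124; at 100 per group Fisher power is only 70.9%.

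Section 7.2 projects 17–18 exposed women per year, which is 119–126 over seven years, and Section 7.7.4 uses a reference threshold of 100 live births. The 4.4 may therefore be left over from a smaller design. That origin is an inference; the protocol does not state it.

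**The case against.** The strongest reply is that this is one stray sentence. Table 7-4 gives the full set of inputs, the Abstract repeats 3.0, and 231 is derived openly, so a careful reader can recover the intended value. The 4.4 drives no sample size, analysis or discontinuation threshold, and it understates the sensitivity of the study. What a null result excludes will depend on the observed confidence interval, which Section 7.7.3.1.1 commits to reporting, and not on a planning value. All of that is fair, and it limits the harm. It does not remove the error: the wrong figure stands in the section that justifies the sample size, and nothing in the protocol says which figure governs.

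A second reply concerns the remedy. The smallest change would set 4.4 to 3.0, because 3.0 is what the design reproduces by the arcsine approximation. This would settle the contradiction but leave the footnote naming Fisher's exact test, under which RR 3.0 has 74.0% power. Moving only the primary row to Fisher would leave Table 7-4 with mixed methods: at 231 per group, the one-sided 1% row would rise from 4.6 to 5.24 and the 10% rows from 1.9 to 1.96. This part of the objection stands and shapes the fix.

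**Conclusion.** The concern holds. For 231 live-birth pregnancies per group, a 3% baseline, two-sided alpha 0.05 and 80% power, the detectable RR is 3.0 to 3.2 depending on the method, and 3.18 under the test the protocol names. The 4.4 in Section 7.5.1 is an error: its power in this design is about 98%. The conclusion rests only on inputs the protocol gives and does not depend on where 4.4 came from.

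The difference between a 2.8% and a 3% baseline is a smaller inconsistency. It moves the Fisher value from 3.18 to about 3.3 and cannot explain 4.4. Because the figure concerns the primary outcome and is simple to correct, it must be fixed.

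**What to change.** In Section 7.5.1, replace 4.4 with the value for 231 per group. Under the footnoted Fisher's exact test that is 3.2 at a 3% baseline, or 3.3 if 2.8% is kept. State the same RR and the same baseline in the Abstract, Section 7.5.1 and Table 7-4.

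If Fisher's test is kept as the named method, recalculate the other rows too. Besides the Table 7-4 rows noted above, the one-sided 1% row of Table 7-5 moves from 4.0 to 4.32, while its primary row stays at 2.7. If the sponsor prefers to keep 3.0, the alternative is to state it at the 3% baseline throughout and change the footnotes to name the arcsine approximation.

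Either route amends text and tables only. Enrolment, recruitment period and analysis do not change. Under the Fisher route, the stated sensitivity becomes slightly less favourable than 3.0.

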**Table 7-4 Sample Size and Detectable Effect Size with 80% Power for Comparison of Exposed Cohort 1 to Unexposed Cohort 2**

Endpoint	N per group	Rate in comparison group	Relative risk	Power
Major structural defects b	231	3%	3.0	80%
Specific pattern of 3 or more minor structural defects	231	1%	4.6	80% c
Spontaneous abortion/still birth	259	10%	1.9	80%

Endpoint	N per group	Rate in comparison group	Relative risk	Power
Preterm delivery	231	10%	1.9	80%
Small for gestational age	231	10%	1.9	80%

aAll tests are two-sided with alpha = 0.05, based on Fisher's exact test, unless specified otherwise. Calculations conducted using R.

bPrimary endpoint; among livebirths.

cOne-sided

**Table 7-5 Sample Size and Detectable Effect Size with 80% Power for Comparison of Exposed Cohort 1 to Unexposed Cohorts 2 and 3 Combined**

Endpoint	N in exposed group	N in comparison group	Rate in comparison group	Relative risk	Power
Major structural defects b	231	462	3%	2.7	80%
Specific pattern of 3 or more minor structural defects	231	462	1%	4.0	80% c
Spontaneous abortion/still birth	259	518	10%	1.7	80%
Preterm delivery	231	462	10%	1.8	80%
Small for gestational age	231	462	10%	1.8	80%

aAll tests are two-sided with alpha = 0.05, based on Fisher's exact test, unless specified otherwise. Calculations conducted using R.

bPrimary endpoint; among livebirths.

cOne-sided

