#### **7.4.3.5 Dysmorphology evaluation**

All live born infants will be eligible for an exam by one of a team of study-dedicated dysmorphologists, led by the study Co-investigator, from the [REDACTED]. The team is made up of licensed pediatricians with subspecialty fellowship training in dysmorphology/genetics. The physical examinations evaluate infants for both major and minor structural defects and provide increased sensitivity for detecting a specific pattern of malformation should one exist. Infants will be examined within the first year of life or as soon as the examination can be practically arranged. The Research Center will group and schedule these follow-up examinations to meet the study criteria of infant age, to maximize physician blinding as to exposure status, and to minimize travel time and expense. The examiner travels to the patient to conduct the examination.

Infant examinations will be conducted using a standard checklist of approximately 130 minor malformations included in a standard physical evaluation form. In addition, with parental consent, digital photographs of the infant will be taken to aid in validating any findings across examiners.

Dysmorphologists will perform these examinations blinded to the exposure or comparison group status of the mothers. Because subjects may have visible evidence of their disease, the use of a disease-matched comparison group allows for preservation of physician blinding. Mothers are asked to sign a consent for medical photographs at the time of the examination. If deemed necessary, the examiners will meet to review photographs of children to assess any patterns that may be identified.

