#### **7.7.2.4 Outcome classification for secondary outcomes**

- ***Spontaneous abortion:*** spontaneous abortion/miscarriage is defined as non-deliberate fetal death which occurs prior to less than 20.0 weeks post-LMP.
- ***Analysis subset:*** the analysis subset for the secondary outcome of spontaneous abortion will be restricted in Cohort 1 to those who were exposed to any dose from

the 4th day post first day of LMP prior to conception to 20 weeks' gestation and enrolled prior to 20 weeks' gestation. The analysis subset for cohorts 2 and 3 will be restricted to those who enrolled prior to 20 weeks' gestation.

- **Stillbirth:** stillbirth is defined as non-deliberate fetal death anytime in gestation at or after 20 weeks post-LMP.
- **Elective termination:** elective termination/abortion is defined as deliberate termination of pregnancy at any time in gestation. Reasons for elective abortions are captured and are classified as due to medical reasons or social reasons.
- **Premature delivery:** premature delivery is defined as live birth prior to 37.0 weeks gestation as counted from LMP (or calculated from first-trimester ultrasound-derived due date if last menstrual period uncertain or more than 1 week discrepant). Elective caesarian deliveries or inductions prior to 37.0 completed weeks will be considered separately.
- **Preeclampsia / eclampsia:** preeclampsia or eclampsia reported by maternal interview with confirmation in medical record or report by medical record only is captured.
- **Small for gestational age:** small for gestational age is defined as birth size (weight, length or head circumference) less than or equal to the 10th centile for sex and gestational age using standard pediatric CDC growth curves for full term or preterm infants (CDC, 2000; Olsen et al., 2010).
- **Minor structural defects:** a minor structural defect is defined as a defect which has neither cosmetic nor functional significance to the child (e.g., complete 2,3 syndactyly of the toes). Minor structural defects will be identified only through the study dysmorphology examination for live born infants using the study-specific checklist.

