#### **8.3.4 Participant information and consent**

The Registry will ensure protection of participant personal data and will not include participant names on any reports, publications, or in any other disclosures, except where required by law.

The informed consent form will be in compliance with the [REDACTED] regulatory requirements.

The informed consent forms used in this study, and any changes made during the course of the study, must be prospectively approved by the [REDACTED] Institutional Review Board (IRB) before use.

The pregnant woman must agree to the oral consent form at the time of enrollment and before completing the intake interview. She must sign an informed consent in order to complete the dysmorphology exam. Each subject will be sent two copies of the written informed consent document following the initial intake interview and requested to sign and return one copy. She must also sign for release of medical information to allow the Registry to obtain information on the pregnancy and the pregnancy outcome from the subject's obstetrician, the hospital of delivery, and any health care specialist, and for the infant from the infant's pediatrician.

The original oral and signed informed consent documents will be maintained by the Registry Office. Original copies of medical record release documents will be retained at the Registry office as well, and the copies will be sent to the institution or physician from whom records are being requested.

Pregnant women under the age of 18 who are eligible for the study and who wish to participate will require written consent of their parent or guardian prior to the initial intake interview and written assent from themselves.

The original oral and signed written informed consent documents and [REDACTED] HIPAA authorizations (applicable to participants receiving healthcare at [REDACTED] or [REDACTED] [REDACTED]) will be maintained by the Registry Office. The original research HIPAA compliant medical record release authorizations will be retained at the Registry office as well, and copies will be sent to the institution or physician from whom records are being requested. These medical release documents are in the authorized format required by [REDACTED] and are compliant with HIPAA regulations.

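### The minor-defect rows of Tables 7-4 and 7-5 count every live-birth pregnancy as examined, and their 80% power is not reached with the Fisher test that the footnote names

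*Protocol*

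**What the plan says.** Section 7.5.1 starts from 867 women in three equal cohorts, 289 each. It allows 10% for spontaneous abortion or stillbirth, 5% for elective abortion and 5% for loss to follow-up, "including 231 pregnancies with at least one live born infant in each cohort at the end of recruitment".

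Table 7-4 then lists "Specific pattern of 3 or more minor structural defects" with 231 per group, a 1% comparator rate, a relative risk of 4.6 and 80% power. Table 7-5 lists the same outcome with 231 against 462, 1%, a relative risk of 4.0 and 80% power. The table footnotes give alpha 0.05 and Fisher's exact test unless specified otherwise, and mark this row as one-sided.

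Section 7.7.2.4 fixes how the outcome is measured: "Minor structural defects will be identified only through the study dysmorphology examination for live born infants using the study-specific checklist". Table 7-1 likewise names the dysmorphology evaluation as its only data source. Enrolment is on oral consent; for the examination, Section 8.3.4 states "She must sign an informed consent in order to complete the dysmorphology exam". On timing, Section 7.4.3.5 says "Infants will be examined within the first year of life or as soon as the examination can be practically arranged".

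Section 7.7.2.5 defines loss to follow-up as a missing outcome interview. Section 7.4.3.7 says that a woman who withdraws after the birth outcome is collected is not counted as lost.

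**The concern.** The N of 231 suits preterm delivery and small for gestational age, which come from maternal report and medical records. A live-born infant who is never examined has no value for the minor-defect outcome, yet remains in the 231, because neither the 5% loss nor any other allowance removes that infant. The tables already vary N by outcome (259 for spontaneous abortion or stillbirth), so an outcome-specific N would fit their layout.

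Two things are at stake. The row may describe a sample larger than the one that will be analysed. The 80% may also not belong to the test named beneath the table. Either would make the study look more sensitive to this listed secondary outcome than it is, and would colour how a null result is read.

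**Working it through.** **Where 231 comes from.** 867 / 3 = 289 per cohort. 289 × (1 − 0.10 − 0.05 − 0.05) = 289 × 0.80 = 231.2. This counts pregnancies with at least one live-born infant. No factor for examination enters.

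**Reproducing the stated 80%.** With the arcsine approximation, power = Φ(h × √(n₁n₂/(n₁+n₂)) − 1.645), where h = 2·arcsin√p₁ − 2·arcsin√p₂ and one-sided alpha is 0.05.

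- Table 7-4: p₁ = 0.046, p₂ = 0.01, h = 0.2320. 0.2320 × √(231/2) − 1.645 = 0.848, so power is 80.2%. The relative risk detectable with 80% power is 4.59, against 4.6 stated.
- Table 7-5: p₁ = 0.04, p₂ = 0.01, h = 0.2024. 0.2024 × √(231 × 462/693) − 1.645 = 0.867, so power is 80.7%. The detectable relative risk is 3.96, against 4.0 stated.

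Both rows reproduce. The same formula gives detectable relative risks of 2.99 and 2.67 for major defects (stated 3.0 and 2.7).

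**The test named in the footnote.** Exact one-sided Fisher power was obtained by summing the binomial probabilities of all outcome pairs with a Fisher p-value of at most 0.05:

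- Table 7-4 (231 against 231, 4.6% against 1%): 69.0%. The relative risk detectable with 80% power is about 5.2.
- Table 7-5 (231 against 462, 4.0% against 1%): 74.0%. The relative risk detectable with 80% power is about 4.3.

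These figures assume that every infant is examined, so the gaps of about 11 points (80.2 − 69.0) and 7 points (80.7 − 74.0) come from the formula alone.

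**Effect of missed examinations.** The protocol gives no completion rate, so the rates below are assumptions, applied equally to all cohorts.

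| Share examined (assumed) | n per group, Table 7-4 | Power at RR 4.6, arcsine | Power at RR 4.6, Fisher | RR for 80% power, Fisher | Table 7-5 power at RR 4.0, arcsine / Fisher |
|---|---|---|---|---|---|
| 100% | 231 | 80.2% | 69.0% | 5.2 | 80.7% / 74.0% |
| 95% | 219 | 78.3% | 66.1% | 5.4 | 78.9% / 71.7% |
| 90% | 208 | 76.4% | 63.2% | 5.6 | 77.0% / 69.6% |
| 80% | 185 | 72.1% | 56.5% | 6.1 | 72.7% / 64.7% |
| 70% | 162 | 67.1% | 49.1% | 6.6 | 67.6% / 59.5% |

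There is almost no slack: by the arcsine formula, Table 7-4 drops below 80% at 229 examined per group (99%) and below 78% at 217 (94%). At 90% examined, the part due to missed examinations in Table 7-4 is about 4 points by arcsine (80.2 − 76.4) and about 6 points by Fisher (69.0 − 63.2).

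**The case against.** Several features favour high completion. Agreement to the examination is an inclusion criterion in all three cohorts (Section 7.2.2.1), the examiner travels to the family, and the timing is flexible (Section 7.4.3.5). At 95% completion the arcsine power is still 78.3% and the detectable relative risk moves only from 4.6 to 4.7. In addition, 231 counts pregnancies. Section 7.7.3.1.2 includes multiple births for this outcome, so infants could slightly outnumber 231, although correlation within a pregnancy limits the gain.

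The consequence is also limited. This is one secondary outcome, its pattern evaluation in Section 7.7.6 is largely a descriptive review, no design decision hangs on the row, and Section 7.9 already concedes limited power.

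These points bear on size and severity, and they stand. They do not supply the missing allowance: agreement at entry is not completion, and withdrawal is permitted at any time.

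A reader might infer from Section 8.3.4 that the examination has its own consent form. The text does not support that. The signature is on the general written study consent sent to every participant after intake; only the photographs have a distinct consent. What holds is that enrolment rests on oral consent and the examination needs a later signature.

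**Conclusion.** The point holds in a limited form. The minor-defect rows use the live-birth N for an outcome observable only in examined infants, and no stated loss covers missed examinations. The 80% is reached only with an arcsine approximation and complete examination. With the named one-sided Fisher test it is 69.0% (Table 7-4) and 74.0% (Table 7-5) at full examination; this rests on the tables' own rates and alpha and needs no completion rate.

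A reader might conclude that missed examinations are what prevents the 80% from being delivered, or might attribute the whole Fisher shortfall to them. The documents support neither. Without a completion rate the examination loss is conditional: about 2 points by arcsine at 95%, about 4 at 90% and about 13 at 70% for Table 7-4. The first 11 points of the Fisher gap in that table have nothing to do with examinations. Severity is minor.

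**What to change.** In the minor-defect rows of Tables 7-4 and 7-5, replace 231 and 231/462 by the expected number of examined infants, and state the assumed completion rate with its source in the investigators' earlier studies. Then restate the detectable relative risk or the power with the footnoted Fisher test, or change the footnote to name the approximation actually used. By Fisher, the Table 7-4 relative risk would be about 5.2 at full examination, 5.6 at 90% and 6.1 at 80%.

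The cost is one restated row in each table and a footnote. Enrolment and conduct do not change. The downside is a less favourable detectable relative risk for one secondary outcome.

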As a secondary approach, a sensitivity analysis will be considered and the following three criteria applied to identify confounders (Xu et al, 2018, Greenland et al, 1999): 1) by assessing each considered variable in a logistic regression model containing the exposure variable and the outcome variable to determine if inclusion of that single covariate changes the estimate of the odds ratio for exposure by 10% or more; 2) standardized mean differences (SMD) greater than 0.1; 3) association with the outcome with p-value < 0.2 in the unexposed cohort (comparison group 2). Care will be taken not to include those variables that are strongly associated with the exposure variable but only weakly associated with the outcome variable (e.g. instrument like variables) (Brookhart et al, 2006). The confounders identified above will be used to build the propensity score (PS) for exposure (Rosenbaum, 2002).

Balance in the covariate distributions before and after weighting will be assessed by providing the standardized mean differences of all covariates.

The primary analysis will be performed using the PS via inverse probability weighting (IPW).

As secondary analysis, the PS will be used in the so-called outcomes regression (Xu et al, 2018, Vansteelandt et al, 2014), i.e. a logistic regression model will be fitted with major structural defect (Y) as outcome, and exposure (A) and logit of propensity score (L) as regressors. In a second step, standardization will be performed to obtain the estimated causal risk ratio (Hernan and Robins, 2019). The CI for the causal risk ratio will be obtained by bootstrap.

Several sensitivity analyses will be performed for the primary outcome of major structural birth defects. One analysis will exclude those defects thought to be of chromosomal or genetic origin. Exposure to a known human teratogen is already included in the list of potential confounders for the siponimod-exposed group vs. comparison group 1. However, in the case where there are insufficient number of events to consider regression adjustment, a sensitivity analysis will be performed excluding participants with exposure to known teratogens in the siponimod-exposed group and comparison group 1 to address this potential confounder.

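### Tables 7-4 and 7-5 attribute their 80% power to Fisher's exact test, but the printed risk ratios match the arcsine approximation; Fisher power for the primary outcome is 74%

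*Protocol*

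**What the plan says.** Protocol section 7.5.1 says that Table 7-4 "gives the minimum detectable effect sizes with 80% power (two-sided significance level 0.05, except as noted below for pattern of minor structural defects"). The footnote to both tables names the method: "All tests are two-sided with alpha = 0.05, based on Fisher's exact test, unless specified otherwise". It adds that the calculations were done in R, and a further footnote marks the minor-defect pattern as one-sided.

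The primary row of Table 7-4 reads "Major structural defects b 231 3% 3.0 80"%, and the minor-pattern row "Specific pattern of 3 or more minor structural defects 231 1% 4.6 80% c". Preterm delivery and small for gestational age (SGA) use 231 per group, 10% and RR 1.9. Spontaneous abortion/stillbirth (SAB/stillbirth) uses 259 per group, 10% and RR 1.9. Table 7-5 pools the two comparison cohorts (231 v 462, or 259 v 518), with RRs of 2.7, 4.0, 1.7, 1.8 and 1.8.

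Two other statements give a detectable effect for the primary outcome at 80% power. The abstract (Study size) gives an RR of about 3.0 "with reference to the baseline prevalence of 2.8% in the Atlanta metropolitan area". The text of section 7.5.1 gives an RR of about 4.4 at a 3% baseline.

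**The concern.** The protocol prints every input to the calculation, so the 80% can be checked without assumptions from outside. At event rates of 1% to 3%, Fisher's exact test is conservative and normal approximations tend to overstate its power. An 80% figure labelled as Fisher therefore needs checking.

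The primary row is the headline property of a registry conducted to meet a post-marketing requirement. If its power is 74.0% rather than 80%, the chance of missing a true threefold risk under the named test is 26.0% rather than 20%. The document would then credit the design with sensitivity that it does not have. Sections that quote the primary figure in different forms would also have no common correct value to refer to.

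**Working it through.** **Inputs.** Group sizes, comparator rates, RRs, sidedness and alpha 0.05 are taken from Tables 7-4 and 7-5 and their footnotes. One-sided alpha for the minor pattern is taken as 0.05. The exposed rate is the comparator rate times RR; for the primary row, 0.03 × 3.0 = 0.09.

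**Step 1: find the method that reproduces the printed figures.** The arcsine normal approximation is

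power = Φ(h·√(n₁n₂/(n₁+n₂)) − z), with h = 2·asin√p₁ − 2·asin√p₀.

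- Primary row: h = 2·asin√0.09 − 2·asin√0.03 = 0.2612. Then √(231·231/462) = 10.747 and the product is 2.807. Power = Φ(2.807 − 1.960) = 80.2%.
- Minor pattern, one-sided: h = 0.2320 and the product is 2.493. Power = Φ(2.493 − 1.645) = 80.2%.

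Solving the same formula for the RR at 80% power:

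| Endpoint | Table 7-4 arcsine | printed | Table 7-5 arcsine | printed |
|---|---|---|---|---|
| Major defects | 2.995 | 3.0 | 2.670 | 2.7 |
| Minor pattern | 4.587 | 4.6 | 3.961 | 4.0 |
| SAB/stillbirth | 1.852 | 1.9 | 1.725 | 1.7 |
| Preterm, SGA | 1.908 | 1.9 | 1.773 | 1.8 |

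Every printed RR is reproduced.

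**Step 2: compute the power of the named test.** Power = Σₓ Σᵧ Bin(x; n₁, p₁)·Bin(y; n₀, p₀)·1[Fisher p(x, y) ≤ 0.05], summed over all outcomes. The two-sided p-value uses the minimum-likelihood rule of R's `fisher.test`; the one-sided row uses the upper tail.

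| Row | Fisher power at printed RR | RR with 80% Fisher power | Printed RR |
|---|---|---|---|
| 7-4 major defects | 74.0% | 3.18 | 3.0 |
| 7-4 minor pattern | 69.1% | 5.24 | 4.6 |
| 7-4 SAB/stillbirth | 80.2% | 1.90 | 1.9 |
| 7-4 preterm, SGA | 75.2% | 1.96 | 1.9 |
| 7-5 major defects | 79.7% | 2.71 | 2.7 |
| 7-5 minor pattern | 74.0% | 4.32 | 4.0 |
| 7-5 SAB/stillbirth | 76.4% | 1.735 | 1.7 |
| 7-5 preterm, SGA | 81.3% | 1.785 | 1.8 |

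**Step 3: ask whether rounding of the RR explains the shortfalls.** The tables fix power and report an RR to one decimal. A row therefore agrees with Fisher if its Fisher-detectable RR rounds to the printed value.

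- Major defects, 7-4: at RR 3.049, the top of the rounding interval, power is still 75.8%.
- Minor pattern, 7-4: at RR 4.649 it is 70.0%.
- Minor pattern, 7-5: at RR 4.05 it is 75.0%.
- Preterm and SGA, 7-4: at RR 1.949 it is 79.3%, and the detectable RR of 1.96 would print as 2.0. The discrepancy is one unit in the last digit.
- The other five rows (SAB/stillbirth in both tables; major defects, preterm and SGA in 7-5) round to the printed RR.

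**Step 4: check the two other statements of the primary figure.** With 231 per group, Fisher power is 70.4% at a 2.8% baseline and RR 3.0 (abstract). It is 98% at a 3% baseline and RR 4.4 (section 7.5.1). Neither is 80%.

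**The case against.** **The footnote may only name the wrong method.** The figures are internally consistent as arcsine results, so correcting the label would remove the contradiction. This stands as one acceptable repair, provided that the lower Fisher power of the primary row is disclosed.

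**A reader might infer that most of the entries are wrong.** They are not. At the tables' precision, five of the ten rows agree with Fisher and two more (preterm and SGA in Table 7-4) miss by the last digit. SAB/stillbirth in Table 7-5 has 76.4% power at exactly 1.7, but its detectable RR of 1.735 still prints as 1.7, so that row needs no change.

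**A reader might also infer a further loss of power because the primary analysis is weighted.** The protocol does say "The primary analysis will be performed using the PS via inverse probability weighting (IPW"), and the tables make no allowance for weighting. But the protocol gives no weight distribution or design effect, and an unadjusted planning calculation contradicts nothing in it. Any figure for this loss would rest on an assumption from outside the documents and is not part of the arithmetic error.

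**The practical consequence is limited.** The analysis of the primary outcome in section 7.7.3.1.1 reports RRs with confidence intervals and does not use Fisher's test. What a null result excludes would be read from the interval, not from planning power. The protocol also says that feasibility shaped the sample size (section 7.5.1) and admits limited power (section 7.9). This is fair, and it rules out the reading that the study's conclusions would be invalid. A general caveat does not, however, correct a specific wrong figure.

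**Conclusion.** The point holds for three rows. Under the test that the tables name, power at the printed inputs is 74.0% for the primary outcome, 69.1% for the minor-defect pattern in Table 7-4 and 74.0% for the minor pattern in Table 7-5, against a stated 80%. Preterm delivery and SGA in Table 7-4 carry a last-digit discrepancy. The other five rows stand. For the primary outcome, the detectable RR moves from 3.0 to about 3.2.

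That the RRs were produced by the arcsine formula is an inference, but a strong one, since it returns every printed value in both tables.

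The result assumes one-sided alpha of 0.05 for the minor pattern and R's two-sided convention. In the 1:1 two-sided rows, doubling the one-sided p-value gives the same power. In the 1:2 rows it gives less: 76.7% instead of 79.7% for major defects in Table 7-5.

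**What to change.** Recompute both tables with Fisher's exact test and restate the detectable RRs:

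- **Table 7-4:** about 3.2 for major defects, 5.2 for the minor pattern (exact 5.24) and 2.0 for preterm delivery and SGA.
- **Table 7-5:** 4.3 for the minor pattern.
- **Other rows:** unchanged.

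Two alternatives are acceptable. One is to keep the RRs and print the true Fisher power beside each. The other is to keep the arcsine figures, name that method in the footnote and state that Fisher power for the primary row is 74%.

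Whichever is chosen, align the abstract (RR about 3.0 at 2.8%) and the RR of 4.4 in section 7.5.1 with the recomputed primary figure, so that the protocol gives one detectable RR for a stated baseline.

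The cost is a recalculation and some rewording. No extra patients are needed; the stated figures become slightly less favourable.
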